The inclusion criteria of the participants will be full-time registered nurses (general) or enrolled nurses (general) who care for adult patients in emergency departments or medical wards. There is no restriction on participants' socio-demographic characteristics, such as gender and age. The exclusion criteria are a nurse who had a professional registration in the psychiatric stream, who does not understand Chinese and English, or who is unable to access or use the internet.

Sample size

According to the systematic review of the effectiveness of interventions in improving the mental health literacy of healthcare professionals in general hospitals, the effect size of an effective intervention ranged from Cohen's $d = 0.75$ to 1.32 . However, the outcomes concern only a particular component of mental health literacy. Therefore, a more conservative effect size, Cohen's $d = 0.5$ was used for estimation of the sample size of the current study. It is estimated using GPower that a sample size of 64 participants per group is adequate to detect an effect size of 0.5 on the primary outcomes at a post-intervention time point with 80% power at a 5% level of significance. Assuming an attrition rate of 15% (Catalogue of Bias Collaboration et al., 2017), this study will recruit 150 nurses (75 per group).

Recruitment

The sampling method will be convenience sampling. Recruitment of participants will be solicited via a public announcement by the poster and electronic mail. The potential subjects will be screened based on the inclusion and exclusion criteria. An information sheet will be sent via electronic mail to the eligible nurses to provide information about the study including its purpose, data collection procedures, etc. In addition, voluntary participation and the right to withdraw from the study freely at any time without any consequences will also be reinforced. Moreover, all participants will be informed that a monetary incentive, a cash coupon of HKD 50, would be given upon completion of all the measurements to compensate for the time spent. Written informed consent will be obtained from the participants before the study's commencement.

Study intervention

The intervention group will receive an educational program consisting of six 30-minutes online educational sessions and followed by one 60-minutes face-to-face session (Refer to Table 1.).

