on the clinical scenarios which can happen in participants' work and are meant to illustrate patients with physical-mental comorbidity in a general hospital who might benefit from psychiatric consultation-liaison service. Through group discussion, participants had to come up with the diagnosis of the case and offer an opinion on action that can be taken by general hospital nurses in helping patients with mental illnesses in general hospitals. In the group sharing, a summary of information about general hospital nurses' mental health literacy obtained in the online education will be presented. Participants can identify the common mental health knowledge deficit, mental illness-related beliefs, and barriers in help-seeking among general hospital nurses who care for patients with mental illnesses. Participants are encouraged to share their personal experiences related to mental health literacy and to explore strategies for dealing with difficulties of caring for patients with mental illnesses in general hospitals, such as how to manage their own emotions when confronted with a challenging scenario. Furthermore, discussions will be guided on further strategies for promoting mental health literacy of healthcare professionals in general hospitals. For this session, the mode of delivery will be changed into zoom meetings according to the situation of disease outbreaks. The total duration of the educational program is 4 hours, and the intervention period will be seven weeks.

The control group will not receive any educational intervention related to mental health

literacy.

Data collection

Before starting the educational program, the socio-demographic data of the participants including age, gender, marital status, education level, occupation, and working years will be collected. The information from participants will be collected through the self-reported form. The collection of these data can provide a more comprehensive picture of the background of the participants and allow initial equivalence among the study groups to be examined.

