Hospital Patient Satisfaction Survey (Huang & Yen, 2015) will be used to assess patient satisfaction with nursing care in general hospitals. There are eight questions on the scale to measure patient satisfaction with nursing care during the hospitalization with a 4-point Likert scale (from "0"=never to "4"=always). The scale had a good psychometric property with a content validity index of .97, item discrimination critical ratio of 28.61 to 50.25, and item correlations ranged from .68 to .84. The exploratory factor analysis with item factor loadings (factors of "professional knowledge and skill" and "environmental control") ranged from .61 to .84, explaining 71.40% of the total variance. The internal consistency was Cronbach's

alpha= .97. (Huang & Yen, 2015).

Data analysis

Statistical analyses

Statistical Package for Social Science will be used for data analysis will be employed for all statistical analyses.

Descriptive statistics were used including means, standard deviations, medians, quartiles, and ranges for age, years of working years, and relative frequencies for gender, marital status, highest education, and occupation. Independent t, Mann-Whitney, chi-square, or Fisher's exact tests, as appropriate, to compare the socio-demographic characteristics between groups. For the outcomes, the generalized estimation equations (GEE) model will be used to examine the intervention effects. Each of the outcomes will be compared between groups with adjustment for potential confounding factors, for example, characteristics of participants shown statistically different between arms at baseline. An intention-to-treat, repeated measures analysis will be conducted to compare changes in the two groups over time. Three effects will be evaluated including the time effect, group effect, and time x group interaction effect. A 2-sided p value less than .05 will be considered statistically significance for all analyses.

Timetable of work

[figure not shown]

Figure 1. Timetable of work

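### Choosing GEE covariates by a significant baseline difference is a poor screen for confounders here; the covariate list, its form of entry and the primary contrast should be fixed in advance

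*Combined protocol and SAP*

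**What the plan says.** Under Statistical analyses, the comparison between groups is made with "adjustment for potential confounding factors, for example, characteristics of participants shown statistically different between arms at baseline". The words introducing the example leave other choices open, but no other method is stated. The tests that would feed the screen are the baseline comparisons in the same section, at the two-sided .05 level set there for all analyses.

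The Data collection section names six characteristics, "including age, gender, marital status, education level, occupation, and working years will be collected". Their stated purpose is to describe the sample and to "allow initial equivalence among the study groups to be examined"; they are not called model covariates. Nothing says how covariates enter the model.

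The target contrast is also open. The Sample size section sets power to "detect an effect size of 0.5 on the primary outcomes at a post-intervention time point". The analysis section says a "repeated measures analysis will be conducted to compare changes in the two groups over time", and adds: "Three effects will be evaluated including the time effect, group effect, and time x group interaction effect".

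Under Study design, a coin toss assigns two hospitals, one to each arm. Under Recruitment, nurses are a convenience sample.

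**The concern.** Nurses are not individually randomised, so real differences between the two groups are plausible and the choice of covariates matters more than in a randomised comparison. A baseline significance test asks whether the sample can show an imbalance. It does not ask whether the factor predicts mental health literacy. A strong predictor can be left out because its imbalance fell short of p<.05, and a factor unrelated to the outcome can be brought in. With no list and no form of entry, covariates can also be chosen after the data are seen. And if the result is time x group while covariates enter as main effects, it could be reported as adjusted although the estimate has not moved.

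**Working it through.** **The plan's own figure.** With d = 0.5, two-sided 5% and 64 per group, the noncentral t test has power 0.8015 (63 per group gives 0.7952), so 64 reproduces. Allowing for 15% attrition, 64/0.85 = 75.3, against the stated 75. Covariate choice does not alter these figures.

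**1. How often the screen misses a true imbalance.** Inputs: 75 per arm (Sample size) and two-sided .05 (Statistical analyses). Miss rate = 1 − power of a two-sample t test with 148 df, critical value 1.976 and noncentrality d√(75/2).

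| True imbalance (SD) | 0.2 | 0.3 | 0.4 | 0.5 |
|---|---|---|---|---|
| Missed | 77% | 55% | 32% | 14% |

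These rates are for a continuous covariate screened on its p-value alone.

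**2. What a covariate main effect does to time x group.** Let D1 and D2 be the between-arm differences at baseline and follow-up, x the covariate difference and b its common slope. With an identity link and complete data, the adjusted contrast is (D2 − bx) − (D1 − bx) = D2 − D1. The covariate cancels, so whether the screen lets it in makes no difference. In simulation with 15% random dropout, bias at the two follow-ups was 0.057 and 0.056 SD without the main effect, and 0.058 and 0.056 with it. The cancellation is not exact if dropout depends on the covariate in one arm only.

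**3. What the screen leaves behind when covariates can act.** Assumptions, none from the documents: true imbalance 0.3 SD; covariate slope 0.3 at baseline and 0.3 + c at both follow-ups, with c = 0 to 0.3; no true effect.

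The imbalance left unadjusted on average is U = d[Φ(h) − Φ(l)] − s[φ(h) − φ(l)]. Here s = √(2/75) = 0.1633 and the significance threshold is 1.976 × 0.1633 = 0.3227. So h = (0.3227 − 0.3)/0.1633 = 0.139 and l = (−0.3227 − 0.3)/0.1633 = −3.813. Then U = 0.3 × 0.5552 − 0.1633 × (0.3951 − 0.0003) = 0.102 SD.

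| Bias in SD | c = 0 | 0.1 | 0.2 | 0.3 |
|---|---|---|---|---|
| Time x group, unadjusted: 0.3c | 0 | 0.03 | 0.06 | 0.09 |
| Time x group, screened covariate x time: 0.102c | 0 | 0.010 | 0.020 | 0.031 |
| Post-intervention difference, unadjusted: 0.3(0.3 + c) | 0.09 | 0.12 | 0.15 | 0.18 |
| Same, screened covariate at that visit: 0.102(0.3 + c) | 0.031 | 0.041 | 0.051 | 0.061 |
| Same, screened main effect pooled over three visits: add 0.198c/3 | 0.031 | 0.047 | 0.064 | 0.081 |

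In the last row 0.198 = 0.3 − 0.102, and c/3 is the shortfall of the pooled slope 0.3 + 2c/3. The upper end of about 0.10 arises at 64 per arm with a main effect pooled over two visits. There U = 0.116, and at c = 0.3 the bias is 0.6 × 0.116 + 0.15 × 0.184 = 0.097. A simulation of 8,000 data sets per setting agrees with these rows to within about 0.002 at 75 per arm. Always including the covariate, with a time term for time x group or at that visit for the post-intervention difference, leaves about 0.

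**The case against.** The strongest reply is that the plan does not rely on adjustment alone. Nurses are measured at baseline and twice afterwards, and a comparison of changes removes stable level differences between the groups, measured or not. This stands. A reader might infer that adjustment is the plan's only control for group differences; the repeated-measures contrast shows that it is not.

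Second, a reader might blame the screen for the whole confounding bias in time x group. With change slopes of 0.1 to 0.3, that contrast has bias of about 0.03 to 0.09 SD and false-positive rates of 6.1% to 11.7% in simulation, depending on the within-nurse correlation. But those figures are the same with or without a covariate main effect, and a fixed list entered as main effects would not change them. They also need a characteristic such as working years to shift scores over about seven weeks even in a control group that receives no education. Nothing in the documents supports that.

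Third, the harm is small. In a single-time-point simulation at 64 per arm, screening held the false-positive rate at 4.5% to 5.7%, against 4.6% to 5.0% with the covariate always included. This also stands, and it limits severity.

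Fourth, the baseline test is given as an example, and four of the six characteristics (gender, marital status, education, occupation) are categorical. The miss rates therefore describe the stated method applied to continuous items, not a certain outcome. The open wording still does not supply a list.

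Last, powering at a post-intervention visit is compatible with a time x group coefficient at that visit, so the two sections do not contradict each other. They leave the choice unmade.

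**Conclusion.** The point holds in a modest form. The one stated selection method is a poor screen for confounders in a two-hospital, non-randomised comparison of nurses, and no list, form of entry or primary contrast is fixed.

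For time x group in the nurse outcomes (identity link, complete data), the screen matters only if covariates enter with time terms. It then leaves about 0.00 to 0.03 SD, at most about 6% of the planned 0.5 SD. For a post-intervention difference it leaves about 0.03 to 0.10 SD, or 6% to 20% of 0.5, against about 0 when the covariate is always included at that visit. These two results belong to different analyses and must not be added.

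The miss rates follow from the plan's own sample size and alpha. The bias sizes rest on assumed imbalances and slopes and are illustrative. The documents do not support the conclusion that the trial's result will be materially biased by the screen. They do support changing it, because a better method costs almost nothing. Confidence is medium.

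**What to change.** Drop selection by baseline p-value and keep the baseline table descriptive. Before outcome data are seen:

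- Name the primary contrast.
- Name a short list of nurse characteristics expected to predict the outcome, from items already collected or known at screening: for example working years, education level, occupation or registration grade, and unit type. Eligibility already depends on the last two, since it requires "full-time registered nurses (general) or enrolled nurses (general) who care for adult patients in emergency departments or medical wards".
- Include all of them whatever their baseline p-value, in a form that acts on the named contrast. For time x group that means covariate x time terms; for a post-intervention difference, the covariates at that visit.
- Report the unadjusted contrast alongside.
- Give patient satisfaction its own short list, because the respondents are patients. If different patients answer in each window, a main effect does move time x group.
- State that nurse-level adjustment cannot remove hospital-level confounding with one hospital per arm.

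Cost: SAP wording, plus recording unit type and, if occupation does not hold it, grade. Sample size is unchanged. With five covariate terms over three visits there are 15 extra parameters. In simulation at 64 per arm the SD of the estimate rises about 2.5% (0.158 to 0.162 at an assumed within-nurse correlation of 0.6). Uncorrected robust standard errors become slightly too small: false positives go from 5.5% to 6.0% at correlation 0.6, and from 5.4% to 6.1% at .797, the scale's quoted test-retest value. The list should therefore stay short.

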This study aims to examine the effect of an educational program on improving the mental health literacy of general hospital nurses, in terms of knowledge of mental health, mental illnesses, and their treatment; attitude or stigma about mental illnesses; and help-seeking efficacy. It also measures the interventional effect on perceived competency in caring for patients with mental illness and work stress among general hospital nurses, as well as patient satisfaction with nursing care in general hospitals.

Study design

This study is a prospective 2-arm parallel controlled trial. Randomized controlled trials

were not feasible for this study because of the risk of contamination (Kahan et al., 2016). It would be difficult to “blind” healthcare professionals to their assigned group because they could easily disseminate information within and between units during clinical sharing or conversation at the common facilities of the same hospital, such as changing rooms and canteen. Two study hospitals will be assigned to the intervention arm or control arm by tossing a coin.

Study setting

The study sites will be conducted in the emergency departments and medical wards of two regional general hospitals. It was because patients with physical-mental comorbidity were mostly caring in this area (Weichert, 2019; Woon & Redzuan, 2019). The two hospitals are similar in nature and the service provided. Both study hospitals provide a comprehensive range of acute, rehabilitation, and ambulatory service for the people living in the western part of the New Territories of Hong Kong. (Pok Oi Hospital, 2022; Tuen Mun Hospital, 2022). These two hospitals had two emergency departments and 18 medical wards, serving about 270,000 patients annually and at least hundreds of nurses were working collaboratively with doctors and allied health in these units (Pok Oi Hospital, 2022; Tuen Mun Hospital, 2022). Indeed, psychiatric consultation-liaison services had been provided in both hospitals since the 1990s.

Eligibility criteria

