In this study, participants will be asked to complete a set of questionnaires including (1) Level of mental health literacy, (2) Perceived competency in caring for patients with mental illnesses, and (3) Level of work stress by online survey. All consenting participants will be assessed at baseline, immediate post-intervention, and one-month post-intervention. Participants from the control group will be assessed on the equivalent dates at the same time points. If there are missing responses to questionnaires completed by participants, the research assistant will follow up via phone or email up to three times to obtain the missing responses.

To examine the interventional effect on the patient satisfaction with nursing care in general hospitals, patients being referred to psychiatric consultation-liaison service at the study sites will

be asked to complete the patient satisfaction survey at baseline (two weeks period before intervention), post-intervention (two weeks period immediate after intervention), and follow-up (two weeks period after one-month post-intervention).

Measurements

Primary outcome: Level of general hospital healthcare professionals' mental health literacy

The level of general hospital healthcare professionals' mental health literacy will be evaluated using The Mental Health Literacy Scale developed by Connor & Casey (2015). This questionnaire comprised 35 items which consisted of the ability to recognize disorders (8 questions), knowledge of where to seek information (4 questions), knowledge of risk factors and causes (2 questions), knowledge of self-treatment (2 questions), knowledge of professional help available (3 questions), attitudes that promote recognition or appropriate help-seeking behavior (16 questions) (O'Connor & Casey, 2015). Questions with a 4-point scale are rated "1" was very unlikely/unhelpful, "4" was very likely/helpful and for a 5-point scale that "1" strongly disagreed/definitely unwilling, "5" strongly agreed/definitely willing. The higher the total score indicates a higher level of mental health literacy. The scale demonstrated good internal and test-retest reliability, and good validity. The Cronbach's alpha of the 35-items scale was .873. Test-retest reliability was $r(69)=.797$, $p<.001$. The scale was significantly positively correlated with

the General Help-seeking Questionnaire total scale of $r(370)=.234, p<.001$.

Secondary outcome: perceived competency in caring for patients with mental illnesses

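### Patient satisfaction reads as serial cross-sections of patients, yet it falls under the repeated-measures, intention-to-treat GEE written for every outcome, with no cluster variable named

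*Combined protocol and SAP*

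**What the plan says.** The section Data analysis, Statistical analyses, excepts no outcome. It states "For the outcomes, the generalized estimation equations (GEE) model will be used to examine the intervention effects", then "Each of the outcomes will be compared between groups with adjustment for potential confounding factors", giving as an example participant characteristics that differ at baseline. It continues "An intention-to-treat, repeated measures analysis will be conducted to compare changes in the two groups over time" and "Three effects will be evaluated including the time effect, group effect, and time x group interaction effect". It names no GEE subject, cluster variable or working correlation. All tests are two-sided at .05.

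Measurements lists patient satisfaction as a secondary outcome; its scale rates nursing care over the hospitalization. Under Data collection the respondents are "patients being referred to psychiatric consultation-liaison service at the study sites", who will "be asked to complete the patient satisfaction survey at baseline (two weeks period before intervention), post-intervention (two weeks period immediate after intervention), and follow-up", the last window being two weeks after one month post-intervention. Study intervention gives an intervention period of seven weeks. Nurses, by contrast, are followed individually through the three assessments.

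Study setting describes "two emergency departments and 18 medical wards, serving about 270,000 patients annually" over the two hospitals, without splitting the units between them. Study design allocates one hospital to each arm by coin.

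**The concern.** The stated analysis suits the three nurse scales, where the same person answers at each time. It does not suit the patient survey, for three reasons.

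- **Repeated measures.** No planned series of answers from the same patient is described.
- **Intention-to-treat.** The term has no defined meaning for patients, who were neither enrolled at the start nor allocated. The hospitals were allocated.
- **Covariates.** The only characteristics described as collected are those of nurses.

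The choice of GEE subject then decides the standard error. Patients on one unit in one window rate much the same nursing team, so their answers may move together. If that is left out, a chance shift in a few units of one hospital can be declared significant at .05. This is the only outcome measured on patients. The unit would be hard to recover later from anonymous, coded forms, so the matter should be settled before the baseline window.

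**Working it through.** **The plan's own figure.** The only sample size is for the nurse primary outcome. A two-sample t-test with d = 0.5, two-sided 5% and 80% power needs 63.8, so 64 per group, as stated. With 15% attrition, 64/0.85 = 75.3, against the stated 75. These figures reproduce but do not bear on the patient survey, which has no sample size.

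**Same patients or different ones?** The first two windows lie on either side of a seven-week programme, and the third follows after a month. The scale covers a hospitalization. The reminders, the chasing of missing responses, the attrition allowance and the coupon are described for the enrolled nurses. Together these point to largely different patients in each window. If re-survey was intended, later answers could rate a stay that preceded the programme.

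**Patients per unit and window.** Inputs are 270,000 patients a year and 20 units (Study setting), and a service utilization of 0.72% to 5.8% (Background).

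- 270,000 × 14/365 = 10,356 patients per window.
- × 0.0072 = 75 referrals; × 0.058 = 601 referrals.
- Divided by 20 units: 3.7 to 30, so about 4 to 30 per unit.

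This assumes that the cited rates apply here, that patients spread evenly over units, and that every referred patient completes the survey.

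**Error rate with the respondent as GEE subject.** Assume k = 10 units per hospital, m patients per unit and window, total variance 1, and a unit-by-window ICC ρ. Stable differences between units cancel in the group-by-window contrast.

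- True variance of a hospital-window mean: [ρ + (1 − ρ)/m]/k = [1 + (m − 1)ρ]/(km).
- Variance assumed with the respondent as subject: 1/(km).
- Understatement factor: f = 1 + (m − 1)ρ.
- Actual false-positive rate: 2[1 − Φ(1.96/√f)].

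| ρ | m | f | false-positive rate |
|---|---|---|---|
| 0 | any | 1.00 | 5.0% |
| .02 | 4 | 1.06 | 5.7% |
| .02 | 10 | 1.18 | 7.1% |
| .02 | 30 | 1.58 | 11.9% |
| .05 | 4 | 1.15 | 6.8% |
| .05 | 10 | 1.45 | 10.4% |
| .05 | 30 | 2.45 | 21.0% |

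Simulation of trials with no true effect agrees: about 6-12% at ρ = .02 and 7-22% at ρ = .05. A t-test on unit-level mean changes stays near 5% in these settings.

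**What the unit-level test cannot remove.** Add a hospital-by-window shift with variance .01 (1% of the total) at ρ = .02. The variance of a unit mean about its hospital is b = .02 + .97/m. The factor becomes f = 1 + 10 × .01/b, judged against t with 18 degrees of freedom (critical value 2.101).

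- m = 4: b = .2625, f = 1.38, error 9.1%.
- m = 10: b = .117, f = 1.86, error 14.0%.
- m = 30: b = .0523, f = 2.91, error 23.4%.

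**The case against.** The strongest reply is that the plan is silent here and does not prescribe an error. Three stronger readings are tempting, and the documents do not support them.

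- **That the patients are certainly different.** Data collection does not say so. A long-stay or re-referred patient could appear twice.
- **That the plan treats patients of one unit as independent.** No GEE subject is named, and a GEE clustered on unit is possible. Independence is the usual result of reading a repeated-measures plan with the respondent as subject; it is not a written choice.
- **That the model cannot be fitted.** The text speaks of change in the two groups. Time, group and their interaction can all be estimated from serial cross-sections with one record per person.

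The list of confounders is also only an example, so patient covariates are not excluded.

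On size, inflation requires units to shift between windows. If unit differences are stable, the contrast's variance is slightly overstated instead: at 10 patients per unit and a total unit ICC of .10, the factor runs from 0.9 with fully stable unit effects to 1.9 with unit effects unrelated between windows. Incomplete response would also push the numbers per unit toward the low end.

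These points limit the claim but do not remove it. No alternative analysis is given for this outcome, no section describes recording a patient's unit, and clustering on hospital would leave two clusters, too few for a robust standard error.

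**Conclusion.** The concern holds as a mismatch between analysis and data, together with an omitted cluster variable. The repeated-measures and intention-to-treat wording does not fit a survey that reads as serial cross-sections, and the usual reading of that wording understates the standard error whenever units shift between windows. Under the assumptions above, the nominal 5% test has a false-positive rate of about 6-12% at ICC .02 and 7-22% at ICC .05, and about 5% if there is no unit-by-window variation. The ICCs, the even split of 10 units per hospital and full survey completion are all assumptions.

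A reader might infer that a unit-level analysis makes the result sound. It does so only if there is no hospital-by-window shift. With one hospital per arm such a shift cannot be told apart from the programme's effect, and one of 1% of variance takes the unit-level test to about 9-23%. The outcome is secondary, so this should be corrected, but it does not touch the primary analysis.

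**What to change.** 1. Take patient satisfaction out of the repeated-measures, intention-to-treat sentence and state whether patients are re-surveyed.
2. Record the unit on the patient form, with a stated rule for patients seen in both the emergency department and a ward, and flag repeat respondents.
3. Analyse the survey as a repeated cross-section with group, window and group-by-window terms. Either compare unit-level mean changes between hospitals, or fit a model with unit and unit-by-window effects and small-sample degrees of freedom.
4. Define the analysis set as completed patient surveys. Do not adjust this outcome for nurse characteristics. If patient covariates are wanted, name them and collect them.
5. Report the outcome as exploratory, giving one hospital per arm as the reason.

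The cost is SAP wording, one or two added items on the patient form (more if patient covariates are collected) and a somewhat wider confidence interval. No extra patients are needed.
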